## **3.2 Secondary objectives and endpoints**

### *Secondary objective 1:*

To evaluate HIV-1 binding antibody responses elicited by CH505 TF chTrimer admixed in 3M-052-AF + Alum or 3M-052-AF (without alum)

### *Secondary endpoint 1:*

Response rate and magnitude of serum IgG binding antibodies as assessed by binding Ab multiplex assay (BAMA)

### *Secondary objective 2:*

To evaluate the ability of the vaccine regimen to elicit HIV-1 specific heterologous tier 2 neutralizing antibodies

### *Secondary endpoints 2:*

Response rate and magnitude of serum antibody neutralization of heterologous HIV-1 strains as measured by TZM-bl assay

## **3.3 Exploratory objectives**

### *Exploratory objective 1:*

To map the epitope specificity of autologous and heterologous tier 2 virus neutralizing activity

### *Exploratory endpoints 1:*

Response rate and magnitude of serum antibody neutralization of epitope knock-out mutants of CH505 TF and heterologous tier 2 viruses

### *Exploratory objective 2:*

Determine the B cell repertoire of peripheral blood B cells in each group of vaccinees

### *Exploratory endpoints 2:*

Detection of induced V3 glycan and CD4 binding site epitope binding antibodies.

### *Exploratory objective 3:*

Determine the transcriptome of vaccine and adjuvant induced peripheral blood immune cells in each group of vaccinees

*Exploratory endpoints 3:*

Detection of origin of V3-glycan and CD4 binding site antibodies from either extrafollicular B cells or follicular B cells.

Additional exploratory objectives:

To conduct analyses related to furthering the understanding of HIV, immunology, vaccines, and clinical trial conduct, including but not exclusive to B cell repertoire analysis (including analysis of rare B cell lineages associated with bnAb precursors), and assessment of lymph node aspirate for germinal center activity, including cellular phenotyping and mutational frequency analysis suggestive of somatic hypermutation and affinity maturation following immunization.

## 4 Laboratory strategy

The primary goal of HVTN 300 is to determine whether the CH505 TF chTrimer immunogen combined with a 3M-052-AF adjuvant can drive the expansion of B cell lineages similar to those known to be associated with broadly neutralizing antibodies induced during natural HIV-1 infection. To this end, HVTN immunogenicity assays will be used to evaluate induction of vaccine and epitope-specific B cells and binding antibodies as well as serum neutralization. These data will also be used to identify and prioritize samples for in-depth immunogenicity analyses, including B cell receptor sequencing of epitope-specific B cells, epitope-mapping of neutralizing antibody responses, and characterization of isolated mAbs. Specifically, flow cytometry will be used to characterize the vaccine-specific B cells using fluorescently-labeled Env probes in both the periphery and the regional lymph node. Furthermore, by using different fluorescently-labeled Env probes with minimal mutations in epitopes of interest, CD4-binding site and epitope-specific lineages of B cells will be identified for downstream analysis. These rare epitope-specific populations of B cells will be enumerated, characterized by surface expression markers, and sorted for BCR sequencing. In addition, the sera from participants will be tested for neutralization not only against the autologous CH505TF pseudovirus, but also a panel of pseudoviruses with engineered mutations specifically designed to identify antibodies that are able to neutralize UCA-sensitive pseudoviruses in an epitope-specific manner. The pace of the development of both B cell isolation techniques and the generation of specific pseudoviruses intended to identify specific antibody lineages is rapid. The laboratory strategy and the technical details are described in the Central Assay Plan and will be updated as new reagents and techniques are incorporated into assay planning. This document will be available on the protocol webpage. Descriptions of the standard HVTN laboratory assays can be found online at <https://www.hvtn.org/en/science.html>.

## 5 Study design

This is an open-label Phase 1 study to examine the safety and immunogenicity of the CH505 TF chTrimer vaccine with 3M-052-AF +/- Alum adjuvant in healthy adults. The primary hypothesis is that the CH505 TF chTrimer will expand CH103-like B-cell precursors.

### 5.1 Study population

All inclusion and exclusion criteria must be met for eligibility. Screening procedures to determine eligibility must be performed within 56 days prior to enrollment.

Investigators should always use good clinical judgment in considering a volunteer's overall fitness for trial participation. Some volunteers may not be appropriate for enrollment even if they meet all inclusion/exclusion criteria. Medical, psychiatric, occupational, or other conditions may make evaluation of safety and/or immunogenicity difficult, and some volunteers may be poor candidates for retention.

#### 5.1.1 Inclusion criteria

1. Able and willing to complete the informed consent process, including an Assessment of Understanding: volunteer demonstrates understanding of this study; completes a questionnaire prior to first vaccination with verbal demonstration of understanding of all questionnaire items answered incorrectly.
2. 18-55 years old, inclusive, on day of enrollment.
3. Available for clinic follow-up through the last clinic visit, willing to undergo lymph node fine needle aspiration and leukapheresis, and willing to be contacted 12 months after the last vaccine administration.
4. Agrees not to enroll in another study of an investigational agent during participation in the trial.
5. In good general health according to the clinical judgement of the site investigator.
6. Physical examination and laboratory results without clinically significant findings that would interfere with assessment of safety or reactogenicity in the clinical judgement of the site investigator.
7. Assessed as low risk for HIV acquisition per low risk guidelines (see [Appendix E](#)), agrees to discuss HIV infection risks, agrees to risk reduction counseling, and agrees to avoid behavior associated with high risk of HIV exposure through the

final study visit. Low risk may include persons stably taking PrEP as prescribed for 6 months or longer.

8. Hemoglobin >12.5 mg/dL to 18 mg/dL
9. White blood cell (WBC) count > 3,500/mm^3
10. Platelets ≥125,000 /mm^3
11. Alanine aminotransferase (ALT) < 2.5 x ULN based on the institutional normal range
12. Serum creatinine ≤1.1 x ULN based on the institutional normal range
13. Blood pressure in the range of 90 to < 160 mmHg systolic and 50 to < 100 mmHg diastolic.
14. Negative results for HIV infection by an FDA-approved enzyme immunoassay (EIA) or chemiluminescent microparticle immunoassay (CMIA).
15. Negative for anti-Hepatitis C antibodies (anti-HCV) or negative HCV nucleic acid test (NAT) if anti-HCV antibodies are detected.
16. Negative for Hepatitis B surface antigen.
17. For a volunteer capable of becoming pregnant:
  - Volunteers who were assigned female sex at birth and are of reproductive potential must agree to use effective means of birth control from at least 21 days prior to enrollment through 8 weeks after their fifth vaccination timepoint (see [Appendix G](#)).
  - Has negative β-HCG (human chorionic gonadotropin) pregnancy test (urine or serum) on day of enrollment.

### **5.1.2 Exclusion criteria**

1. Volunteer who is breast-feeding or pregnant.
2. Previous or current recipient of an investigational HIV vaccine (previous placebo recipients are not excluded).
3. Systemic glucocorticoid use equal to or greater than prednisone 10 mg/day within 3 months prior to enrollment, congenital or acquired immunodeficiency or other systemic medication use likely to impair immune response to vaccine in the opinion of the site investigator.

4. Blood products or immunoglobulin within 16 weeks prior to enrollment; receipt of immunoglobulin within 16 weeks prior to enrollment requires PSRT approval.
5. Receipt of any live attenuated vaccine within 4 weeks prior to enrollment.
6. Receipt of any vaccines that are not live attenuated within 14 days prior to enrollment; replication incompetent vaccines such as the Jynneos vaccine for the prevention of monkeypox disease are not considered to be live vaccines.
7. ACAM2000 vaccine for Monkeypox received within 30 days prior to enrollment or receipt of study product, or if ACAM2000 received greater than 30 days prior to enrollment or receipt of study product, vaccination scab still present; or planned administration within 30 days after enrollment or receipt of study product.
8. Initiation of antigen-based immunotherapy for allergies within the previous year (stable immunotherapy is not exclusionary); inclusion of participants who initiated immunotherapy within the previous year requires PSRT approval.
9. Receipt of investigational research agents with a half-life of 7 or fewer days within 4 weeks prior to enrollment. If a potential participant has received investigational agents with a half-life greater than 7 days (or unknown half-life) within the past year, PSRT approval is required for enrollment.
10. Serious reactions to vaccines that preclude receipt of study injections as determined by the principal investigator or designee. History of serious reaction (eg. hypersensitivity, anaphylaxis) to any vaccine or any component of the study vaccine, including imidazoquinolone (eg, imiquimod).
11. Hereditary angioedema, acquired angioedema, or idiopathic forms of angioedema.
12. Idiopathic urticaria within the past year.
13. Bleeding disorder diagnosed by a doctor (eg, factor deficiency, coagulopathy, or platelet disorder requiring special precautions).
14. Seizure disorder; febrile seizures as a child or seizures secondary to alcohol withdrawal more than 5 years ago are not exclusionary.
15. Asplenia or functional asplenia.
16. Active duty and reserve US military personnel.
17. Any other chronic or clinically significant condition that in the clinical judgement of the investigator would jeopardize the safety or rights of the study participant, including, but not limited to: clinically significant forms of drug or alcohol abuse,

serious psychiatric disorders, or cancer that, in the clinical judgement of the site investigator, has a potential for recurrence (excluding basal cell carcinoma).

18. Asthma is excluded if the participant has ANY of the following:
  1. Required either oral or parenteral corticosteroids for an exacerbation two or more times within the past year; OR
  2. Needed emergency care, urgent care, hospitalization, or intubation for an acute asthma exacerbation within the past year (eg, would NOT exclude individuals with asthma who meet all other criteria but sought urgent/emergent care solely for asthma medication refills or co-existing conditions unrelated to asthma); OR
  3. Uses a short-acting rescue inhaler more than 2 days/week for acute asthma symptoms (ie, not for preventive treatment prior to athletic activity); OR
  4. Uses medium-to-high-dose inhaled corticosteroids (greater than 250 mcg fluticasone or therapeutic equivalent per day), whether in single-therapy or dual-therapy inhalers (ie, with a long-acting beta agonist [LABA]);
  5. Uses more than one medication for maintenance therapy daily. Inclusion of anyone on a stable dose of more than one medication for maintenance therapy daily for greater than two years requires PSRT approval.
19. A participant with a history of an immune-mediated disease, either active or remote. Specific examples are listed in [Appendix H](#) (AESI index). Not exclusionary: 1) remote history of Bell's palsy (>2 years ago) not associated with other neurologic symptoms, 2) mild psoriasis that does not require ongoing systemic treatment
20. History of allergy to local anesthetic (Novocaine, Lidocaine).
21. Investigator concern for difficulty with venous access based upon clinical history and physical examination. For example, history of IV drug abuse or substantial difficulty with previous blood draws.

## **5.2 Participant departure from vaccination schedule or withdrawal**

### **5.2.1 Delaying vaccinations for a participant**

Under certain circumstances, a participant's scheduled vaccination will be delayed. The factors to be considered in such a decision include but are not limited to the following:

- Intercurrent illness or pre-vaccination abnormal vital signs or clinical symptoms that may mask assessment of vaccine reaction

- Treatment with systemic glucocorticoids (eg, prednisone or other glucocorticoid), immune targeting monoclonal antibodies or other immunomodulators (other than nonsteroidal anti-inflammatory drugs [NSAIDs]), with the exception that study injection may continue per PI discretion if the next study injection occurs at least 2 weeks following completion of glucocorticoid treatment;
- Receipt of any live attenuated vaccines within 4 weeks prior to study vaccine administration; (Note: ACAM2000 vaccine for Monkeypox received within 30 days prior to enrollment or receipt of study vaccine; or if ACAM2000 received greater than 30 days prior to enrollment or receipt of study vaccine and vaccination scab still present; or planned administration within 30 days after enrollment or receipt of study vaccine).
- Receipt of any vaccines that are not live attenuated vaccines within 2 weeks prior to study vaccine administration. Replication incompetent vaccines such as the Jynneos vaccine for the prevention of monkeypox disease are not considered to be live vaccines.

Vaccinations should not be administered outside the visit window period specified in [Appendix C](#) without PSRT approval.

## **5.2.2 Discontinuation of study vaccine administration**

Under certain circumstances, an individual participant's vaccinations will be permanently discontinued. Specific events that will result in stopping a participant's vaccination schedule include:

- SAE that is subsequently considered to be related to vaccination
- Pregnancy (regardless of outcome)
- HIV infection
- Grade 3 AE assessed as related to study vaccine with the exception of fever and subjective local and systemic symptoms. For grade 3 injection site erythema and/or induration, upon review, the PSRT may allow continuation of vaccination (except with review by the PSRT)
- Grade 4 AE assessed as related to study vaccine
- Clinically significant type 1 hypersensitivity associated with study vaccine

For ease of reference and review, the clinically significant type 1 hypersensitivity definition, as per the Second National Institute of Allergy and

Infectious Disease/Food Allergy and Anaphylaxis Network symposium criteria for anaphylaxis (25), is provided below:

1. Acute onset of an illness (minutes to several hours) with involvement of the skin, mucosal tissue, or both (eg, generalized hives, pruritus or flushing, swollen lips-tongue-uvula)

AND AT LEAST ONE OF THE FOLLOWING:

a. Respiratory compromise (eg, dyspnea, wheeze-bronchospasm, stridor, reduced PEF, hypoxemia)

b. Reduced BP or associated symptoms of end-organ dysfunction (eg, hypotonia [collapse], syncope, incontinence)

2. Two or more of the following that occur rapidly after exposure to a likely allergen for that patient [participant] (minutes to several hours):

a. Involvement of the skin-mucosal tissue (eg, generalized hives, itch-flush, swollen lips-tongue-uvula)

b. Respiratory compromise (eg, dyspnea, wheeze-bronchospasm, stridor, reduced PEF, hypoxemia)

c. Reduced BP or associated symptoms (eg, hypotonia [collapse], syncope, incontinence)

d. Persistent gastrointestinal symptoms (eg, crampy abdominal pain, vomiting)

3. Reduced BP after exposure to known allergen for that patient [participant] (minutes to several hours). Adults: systolic BP of less than 90 mm Hg or greater than 30% decrease from that person's baseline

- PI assessment that it is not in the best interest of the participant to continue receiving study vaccine.
- Newly disclosed AESI (see [Appendix H](#))
- Co-enrollment in a study with an investigational research agent (rare exceptions allowing for the continuation of vaccinations may be granted with the unanimous consent of the HVTN 300 PSRT)

Participants discontinuing study vaccine for reasons other than HIV infection should be encouraged to participate in follow-up visits and procedures per the protocol for up to 12 months following their last study vaccine administration. At the discretion of the CRS clinician and the PSRT (for composition of PSRT see

Section 9.3), some clinic procedures and sample collections may be modified or discontinued.

If a participant becomes HIV-infected during the course of the study, no additional study vaccine will be administered. Participants will be encouraged to continue scheduled study visits for up to 12 months following their last study vaccine administration or until the final scheduled clinic visit, whichever comes first. At post-infection follow-up visits, only samples for protocol-specified clinical labs (with the exception of HIV diagnostic testing) will be collected. In addition, some clinic procedures may be modified or discontinued.

### **5.2.3 Participant departure from vaccine schedule**

If a participant misses a scheduled vaccination, they are eligible for future vaccinations.

### **5.2.4 Discontinuation of study participation**

A participant may be discontinued from protocol participation for the following reasons:

- Participant voluntarily withdraws;
- CRS determines the participant is lost to follow-up;
- The IND Sponsor or regulatory authorities stop the study; or,
- PI assessment that it is not in the best interest of the participant to continue participation in the study or that the participant's compliance with the study is not sufficient.

If a participant terminates participation in the study early for any reason, the site principal investigator should consider if the following assessments are appropriate: end-of-study HIV test, CBC with differential, serum chemistry, physical examination, and if indicated, a pregnancy test (see [Appendix A](#) and [Appendix B](#)). For participants with HIV infection, please see Section 8.7. If the site principal investigator has questions regarding a termination visit they should consult with the PSRT.

## 6 Statistical considerations

### 6.1 Sample size justification and accrual

Recruitment will target enrolling a total of 48 healthy, HIV-uninfected adult participants in 4 groups.

In Part A, recruitment will target enrolling 12 healthy, HIV-uninfected adult participants in Group 1. The protocol team will convene after the 12th participant has received their third vaccination to determine if further participants should be enrolled to evaluate immunogenicity. Examples of reasons that might necessitate enrollment of additional participants are provided in Section 1.5. If some participants from the original number of 12 enrolled will not contribute data to some of the immunogenicity analyses, the protocol team may enroll additional fully evaluable participants, up to 6 additional participants, or a total of 18 participants enrolled, with the goal of at least 12 contributing to the final immunogenicity analyses.

In Part B, recruitment will target enrolling a total of 36 healthy, HIV-uninfected adult participants in Groups 2, 3, and 4 ( $n = 12$  participants per group). Enrollment in Groups 2, 3, and 4 will be stepwise by group, starting with Group 2, continuing with Group 3, and finishing with Group 4.

Every study participant will be followed for an AESI contact 12 months after the last vaccination received (for example, following participants until Month 16 if they receive 3 vaccinations, or Month 24 if they receive 5 vaccinations).

Detail about the pace of enrollment can be found in Section 1.5.

Since enrollment is concurrent with receiving the first vaccination, all participants will provide some safety data. However, for immunogenicity analyses, data may be missing for a variety of reasons, including participants terminating from the study early, problems in shipping specimens, or high assay background. Immunogenicity data from 17 Phase 1 and 2 Phase 2a HVTN vaccine trials, which began enrolling after June 2005 (data as of September 2014), indicate that 17% is a reasonable estimate for the rate of missing data.

#### 6.1.1 Power calculations for immunogenicity for Part A

One primary goal of the statistical analysis for Part A is to assess whether the vaccine regimen evaluated in Group 1 elicits CD4 binding-site, V2 apex and V3 glycan epitope (bnAb region at the base of the V3 loop), and CH505TF-specific memory B cells. The primary endpoint will be the frequencies of CD4 binding-site, V2 apex and V3 glycan epitope (bnAb region at the base of the V3 loop), and CH505TF-specific IgG+ B cells at baseline and after vaccination, as measured by flow cytometry. Another primary goal is to evaluate the ability of the vaccine

regimen to elicit autologous tier 2 virus neutralizing antibodies, as measured using the TZM-bl assay.

The statistical analysis will first compare the frequencies of CD4 binding-site, V2 apex and V3 glycan epitope, and CH505TF-specific IgG+ B cells at baseline with those observed after vaccination. These comparisons will use Wilcoxon signed-rank tests. Should the vaccine regimen elicit a desired immune response, we expect the frequencies of CD4 binding-site or V2 apex or V3 glycan epitope or CH505TF-specific IgG+ B cells to increase after vaccinations, and the tests will be one-sided. An additional analysis will compare the frequencies of CD4 binding-site, V2 apex and V3 glycan epitope, and CH505TF-specific IgG+ B cells at different time points after vaccination using two-sided Wilcoxon signed-rank tests.

The statistical analysis will also perform response positivity calls for each study participant by comparing B cells frequencies at baseline to B cells frequencies post-vaccination using Fisher's exact tests. The statistical analysis will next assess whether the frequencies of CD4 binding-site, V2 apex and V3 glycan epitope, and CH505TF-specific IgG+ B cells differ between time points post-vaccination. These comparisons will be performed using two-sided Fisher's exact tests.

We will next estimate the response rate at each post-vaccination time point by the empirical proportion of positive calls among study participants and build an associated 95% confidence interval.

[figure not shown]
We computed the power of a one-sided Wilcoxon signed-rank to detect a significant difference between the frequencies of CD4 binding-site, or V2 apex or V3 glycan epitope (bnAb site at the base of the V3 loop), or CH505TF-specific IgG+ B cells observed at baseline with that observed at one time point post-vaccination. The power was evaluated as a function of (1) the effect size, defined here as the average change (increase) in the frequencies of (eg) CD4 binding-site or V3 glycan (base of the V3 loop) binding-IgG+ B cells after vaccination relative to baseline, and (2) the standard deviation (SD) of the difference between pre- and post-vaccination frequencies. The calculations made the following assumptions:

- The average increase in the frequency of CD4 binding-site IgG+ B cells post-vaccination relative to baseline in study participants ranges between 0 and 5%.
- The standard deviation of the frequency of CD4 binding-site IgG+ B cells post-vaccination relative to baseline in study participants ranges between 0.5% and 4%.
- The increase in the frequency of CD4 binding-site IgG+ B cells after vaccination relative to baseline is normally distributed. Departure from this assumption is not expected to impact the power of the study because the Wilcoxon signed-rank test is nonparametric.

The calculations considered samples of size  $n = 12$  and  $n = 10$  to assess power when the data set is complete ( $n = 12$ ) and when 2 out of the 12 participants (or, equivalently, an attrition rate of approximately 17%;  $n = 10$ ) are lost to follow up before the post-vaccination time point.

The power function of the test under these different scenarios is presented in [Figure 6-1](#). For example, if the standard deviation of the change in the frequency of binding IgG+ B cells is  $SD = 2\%$ , the calculation indicates that a sample of size  $n = 10$  achieves almost 80% power to detect a significant increase at the 5% significance level if the average increase in the proportion of binding IgG+ B cells is 1.5%. With a sample of size  $n = 12$  (no loss to follow-up), the test has more than 80% power to detect a significant difference under the same scenario.

**Figure 6-1** Power of a one-sided Wilcoxon signed-rank test comparing the frequency of CD4 binding-site or V2 apex or V3 glycan epitope (bnAb site at the base of the V3 loop) CH505TF-specific IgG+ B cells post-vaccination relative to baseline. The power was calculated as a function of (1) the effect size, defined as the average difference between the frequencies of B cells pre- and post-vaccination; (2) the standard deviation (SD) of the difference between the pre- and post-vaccination B cell frequencies; and (3) the sample size ( $n = 10$  and  $n = 12$ ).

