## **2.7 Rationale for Leukapheresis**

To assess the expansion of rare precursor B cell populations that occur at a frequency of approximately  $\sim 1/20$  million cells, large numbers of peripheral blood mononuclear cells (PBMCs) are required. Leukapheresis can provide 6-10 billion PBMCs without depleting red blood cells or other blood components. There are approximately 1 million PBMCs per milliliter of blood and therefore peripheral blood sampling at volumes associated with typical blood donation ( $\sim 500$  mL) would not provide sufficient PBMC numbers. Furthermore,

leukapheresis is associated with fewer adverse events when compared to blood donation. Hence this protocol will employ leukapheresis in study participants enrolled in Part A ([Appendix A](#)) to ensure adequate specimens for analysis of rare precursors. Leukapheresis will be performed at screening and after the 4th dose of CH505 TF chTrimer has been administered. The rationale for performing leukapheresis three weeks after the 4th dose is based upon detailed preclinical investigations into the kinetics of the germinal center response in rhesus macaques (see Section [2.1](#) and (24)).

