### 6.1.2 Power calculations for immunogenicity for Part B

The goal of Part B is to evaluate whether the three vaccine regimens tested in Groups 2, 3, and 4 elicit CD4 binding-site, V2 apex and V3 glycan epitope (bnAb region at the base of the V3 loop), and CH505TF-specific memory B cells. The primary endpoint will be the frequencies of CD4 binding-site, V2 apex and V3 glycan epitope (bnAb region at the base of the V3 loop), and CH505TF-specific IgG+ B cells at baseline and after vaccination, as measured by flow cytometry. Part B will also evaluate whether the vaccine regimens elicit autologous tier 2 virus neutralizing antibodies using the TZM-bl assay.

The statistical analysis will first compare the frequencies of CD4 binding-site, V2 apex and V3 glycan epitope, and CH505TF-specific IgG+ B cells at baseline with those observed after vaccination. These comparisons may be performed within each treatment group (ie, Group 2, 3, and 4) using Wilcoxon signed-rank tests. Should the vaccine regimens elicit a desired immune response, we expect the

frequencies of CD4 binding-site or V2 apex or V3 glycan epitope or CH505TF-specific IgG+ B cells to increase after vaccinations, and the tests will be one-sided. Additional analyses will compare the frequencies of CD4 binding-site, V2 apex and V3 glycan epitope, and CH505TF-specific IgG+ B cells at other time points following vaccination; these tests will be two-sided because the direction of the effect may not be known.

The statistical analysis will also perform response positivity calls for each study participant by comparing B cells frequencies at baseline to B cells frequencies post-vaccination using Fisher's exact tests. The statistical analysis will next assess whether the frequencies of CD4 binding-site, V2 apex and V3 glycan epitope, and CH505TF-specific IgG+ B cells differ between time points post-vaccination. These comparisons will be performed using two-sided Fisher's exact tests. We will next estimate the response rate at each post-vaccination time point within each group by the empirical proportion of positive calls among study participants. Associated 95% confidence intervals will also be built.

[figure not shown]

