## 6.2 Statistical analyses

This section describes the final study analysis, unblinded as to treatment arm assignment. All data from enrolled participants will be analyzed regardless of how many vaccinations they received. All analyses will be performed using SAS and R.

No formal multiple-comparison adjustments will be employed for multiple safety endpoints, multiple primary immunogenicity endpoints, or secondary endpoints. Statistical tests for comparisons of primary and secondary endpoints, including two- and one-sided tests, will use a significance level (alpha) of 5%.

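### The per-participant Fisher's exact call for B-cell positivity has no term for visit-to-visit variation, so the reported B-cell response rate can be inflated

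*Protocol*

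**What the plan says.** Protocol section 6.1.1 (Part A) states that the analysis will "perform response positivity calls for each study participant by comparing B cells frequencies at baseline to B cells frequencies post-vaccination using Fisher's exact tests". It will then "estimate the response rate at each post-vaccination time point by the empirical proportion of positive calls among study participants" and attach a 95% confidence interval. Section 6.1.2 gives Groups 2 to 4 the same rule, again "comparing B cells frequencies at baseline to B cells frequencies post-vaccination using Fisher's exact tests".

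Neither section adds a minimum rise, a minimum cell count, a background threshold or a replicate-based variance. Neither says whether the call is one- or two-sided. The two-sided wording, "These comparisons will be performed using two-sided Fisher's exact tests", belongs to the comparison between post-vaccination time points.

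Section 6.2 says that tests of primary and secondary endpoints, "including two- and one-sided tests, will use a significance level (alpha) of 5" per cent. It also says: "No formal multiple-comparison adjustments will be employed for multiple safety endpoints, multiple primary immunogenicity endpoints, or secondary endpoints". Reading 5% as the threshold for individual calls is an inference, but no other threshold is given.

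Section 6.2.2 leaves assay detail to the SAP, and section 4 leaves technical detail to the Central Assay Plan. The supplied SAP limits itself to safety and tolerability (its sections 2 and 4) and has no positivity rule.

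**The concern.** A positivity call is meant to answer whether this participant responded to the vaccine. With one participant and two samples, Fisher's exact test needs counts, so each cell becomes an independent observation. The hypothesis tested is that both samples come from exactly the same cell frequency. Biological fluctuation, staining, gating and batch differences between visits weeks or months apart are outside that null. The more cells are counted, the more readily such differences reach significance.

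The design offers no internal check on this. There is no placebo product (section 9.2.1), so no concurrent estimate of the false-call rate. In Part A the baseline cells come from leukapheresis at screening (section 8.1), while most later PBMC samples in Appendix A are blood draws. That is a further difference unrelated to vaccine.

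Three uses of the calls are exposed: the reported response rates, any Barnard comparison with other CH505 candidates that uses them (section 6.2.2), and the choice of responders and samples for further assays and sequencing (sections 2.9 and 4).

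**Working it through.** The plan states no false-call rate, cell count or visit-to-visit CV, so there is no figure of its own to reproduce.

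**Inputs from the documents.** Group size is 12: "recruitment will target enrolling 12 healthy, HIV-uninfected adult participants in Group 1", and the same number in each of Groups 2 to 4. PBMC yield: "There are approximately 1 million PBMCs per milliliter of blood" (section 2.7). A typical blood draw for PBMC is 136 mL (Appendices A and B), so about 136 million PBMC.

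**Assumptions, not in the documents.** IgG+ B cells are about 1% of PBMC. A stain of 10 million PBMC then gives about 100,000 of them, and a whole draw about 1 million. The target population is 0.01% to 1% of IgG+ B cells. Visit-to-visit CV is 0 to 50%, with log-normal variation.

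**Hand formula.** Let x be the expected positive cells per visit, with equal cell numbers at both visits and no vaccine effect. The log ratio has true variance of about 2/x + 2 ln(1+CV²). Fisher's test uses only the 2/x part. So for a one-sided 5% call:

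false-call rate ≈ 1 − Φ(1.645 × √[(2/x) / (2/x + 2 ln(1+CV²))])

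Example, x = 100 and CV 30%: 2/x = 0.020 and 2 ln(1.09) = 0.172. The root is √(0.020/0.192) = 0.322, and 1 − Φ(0.530) = 0.30.

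**Simulation.** Log-normal visit frequencies, binomial counts, exact hypergeometric tail:

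| Expected positive cells | Example | CV 20%: formula / simulated | CV 30%: formula / simulated |
|---|---|---|---|
| 5 | 0.01% of 50,000 | 7% / 3% | 8% / 5% |
| 20 | 0.1% of 20,000 | 11% / 9% | 16% / 14% |
| 100 | 0.1% of 100,000 | 23% / 22% | 30% / 29% |
| 1,000 | 1% of 100,000 | 40% / 39–40% | 43% / 42–43% |

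- At CV 0 the simulated rate never exceeds 5%, so the missing variance term is the cause. At small counts the exact test is more conservative than the formula. As x grows the limit is 50%.
- Counting only increases from a two-sided 5% test, about 100 cells gives about 18% at CV 20% and 25–26% at CV 30%.
- A stricter threshold alone is not a cure: at 100 cells, alpha 0.001 still gives 8%, 16% and 25% at CV 20%, 30% and 50%.
- If the baseline sample holds ten times as many cells, 20 post-vaccination cells give 14% and 20% at CV 20% and 30%.

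**Effect on a group of 12.** With false-call rate f, the expected number of false responders when nobody responds is 12f, and P(3 or more) = 1 − Σ C(12,k) fᵏ(1−f)¹²⁻ᵏ over k = 0, 1, 2.

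- f = 5%: 0.6 expected, P = 0.02.
- f = 20%: 2.4 expected, P = 0.44.
- f = 30%: 3.6 expected, P = 1 − (0.014 + 0.071 + 0.168) = 0.75.

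If all true responders are called, the reported rate is π + (1−π)f. At f = 30%, a true 25% reads 0.25 + 0.75 × 0.30 = 47.5%, and a true 75% reads 82.5%.

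**The case against.** **The populations may be too rare for this to matter.** Section 4 calls the epitope-specific cells rare, and section 2.7 puts bnAb precursors at about 1 in 20 million cells. On that figure a 136-million-PBMC draw holds 136/20 ≈ 7 such cells. At counts this low the test is conservative or nearly so. This stands as a limit on size. That frequency is for precursors, though, not necessarily for the endpoint populations, which include all CH505TF-specific IgG+ B cells. The planning assumptions in section 6.1.1 also consider average rises of up to 5 percentage points, far from rare. Nothing in the plan keeps the call in the low-count region.

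**The rule may be completed elsewhere.** An immunogenicity analysis plan or the Central Assay Plan could add a minimum rise, so the absence is shown only for the supplied documents. Even so, the protocol states a concrete rule, and followed as written it can give a wrong rate. That is more than missing detail.

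**The primary analysis is elsewhere.** Primary endpoint 1 is the frequency (section 3.1), compared first by Wilcoxon signed-rank tests across participants. Those tests use the participant as the unit and are not affected in this way. The Barnard comparison is optional and does not name the B-cell calls. Both points stand.

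**A stronger reading to avoid.** A reader might infer that the response rate is certainly inflated, by 20 to 45 points among non-responders. The documents do not support that: they give neither counts nor CV, and the low-count rows show no excess. Nor should every rejection of a two-sided test be counted as a false response, since about half would be decreases.

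**Conclusion.** The concern holds in conditional form. Because the Fisher null contains cell-sampling error only, variation between visits can be called a response, and the B-cell response rate and its confidence interval can be inflated.

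The excess is material from about 20 positive cells with a CV of 20% or more. It is absent at about 5 cells or fewer with equal sample sizes and CV up to 30%; at CV 50% the rate at 5 cells is about 8%. All these sizes rest on assumed counts and CVs. The SD of change used for planning in section 6.1.1 (0.5% to 4%) is only an upper guide to visit-to-visit variation, because it may include differences in vaccine response.

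The response rates and what is built on them are affected. The frequency-based analysis of primary endpoint 1 is not.

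**What to change.** In sections 6.1.1 and 6.1.2 and in the immunogenicity analysis plan, define a positive call as an increase with one-sided Fisher p < 0.05 **and** a post/baseline frequency ratio at or above a pre-set bound, for example 2-fold. Alternatively, use an overdispersed (beta-binomial) test. Report response rates from that call.

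Set the bound or the overdispersion before analysis from existing repeat-sample data, using data that include biological as well as assay variation where available. Repeat runs of control PBMC alone capture staining, gating and batch effects but not biological change between visits.

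**What a 2-fold bound does.** The chance that the ratio reaches 2 with no effect is about 1 − Φ(ln 2 / √[2/x + 2 ln(1+CV²)]).

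- At x = 100: 1 − Φ(0.693/0.314) ≈ 1% at CV 20%, and 1 − Φ(0.693/0.439) ≈ 6% at CV 30%.
- Simulation gives about 1–2% at CV 20% and 5–6% at CV 30%, with 100 or more positive cells.
- At about 20 cells the observed ratio is itself noisy and the bound removes less, leaving about 10% at CV 30%.

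An overdispersed test suits the lower counts better. In simulation, adding a known visit-to-visit variance term to a log-ratio test returned the rate to 4.6–5.1% at expected counts of 20 to 500 and CV 10–50%. Having to estimate that variance would make this less exact.

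**Cost.** Wording and minor programming, with no new trial samples. Some modest true rises are no longer called: with 100,000 cells and CV 20–30%, a 2-fold bound keeps about 71–78% of 1.5-point rises from a 1% baseline, and 100% of the same rises from a 0.1% baseline.
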